### 1.3 Schedule of Assessments

Procedures/assessments	Visit 1 Screen (Week -6)	Run-in Period Compliance Calls	Visit 2 Week 0	Visit 3 Week 6	Visit 4 Week 12
Informed consent	X				
Review inclusion/exclusion criteria	X		X		
Review medical history	X				
Review daily exercise habits	X				
Review concomitant therapies	X		X	X	X
Biometrics: Height*, weight, waist and hip circumference, heart rate, blood pressure, respiratory rate, and temperature	X		X	X	X
*only be measured at Visit 1					
Urine pregnancy test	X		X		
Physical examination			X		
Randomization			X		
CBC, Na, K, Cl, Fe, Mg, Ca, phosphate, HbA1c, fasting glucose, eGFR, creatinine, BUN, AST, ALT, GGT, ALP, TSH* and total bilirubin	X		X		X
*only be measured at Visit 1					
Blood Collection: lipid profile and fasting insulin	X		X		X
Urinalysis	X		X		X
DXA			X		X
BIA	X		X		
Stool Collection Kits Dispensed	X			X	
Stool Collection Kit Returned			X		X
Exercise Guideline Review	X	X	X	X	
Daily Bowel Habits Diary Dispensed	X		X	X	
Daily Bowel Habits Diary Returned			X	X	X
3DFR Dispensed	X		X	X	
3DFR Returned			X	X	X
Exercise Diary Dispensed	X		X	X	
Exercise Diary Returned			X	X	X
Subject Diary Dispensed	X		X	X	
Subject Diary Returned			X	X	X
Placebo Dispensed		X			
Placebo Returned			X		
IP Dispensed			X	X	

Procedures/assessments	Visit 1 Screen (Week -6)	Run-in Period Compliance Calls	Visit 2 Week 0	Visit 3 Week 6	Visit 4 Week 12
IP Returned				X	X
Compliance Calculated			X	X	X
Adverse Events		X	X	X	X

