#### *Removal by Qualified Investigator*

Protocol 20BWHM:

A randomized, double-blind, placebo-controlled study to investigate the effects of a *Bifidobacterium breve* strain on fat loss in healthy adults

Participant discontinuation should be considered at the discretion of the qualified investigator. The circumstances of any discontinuation must be documented in detail in the participant file and final report. If possible, the evaluations planned for the end of treatment will be carried out at the time when the participant is withdrawn from the study.

Criteria for removal of participants from the study includes:

*Clinical reasons*

A participant may be withdrawn from the study if, in the opinion of the qualified investigator, it is not in the participant's best interest to continue. Any participant who experiences a serious adverse event (SAE) may be withdrawn from the trial at the discretion of the qualified investigator. A participant will also be withdrawn due to adverse events causing clinically significant illness or the need for prohibited medication(s) during the trial. Any female participant who becomes pregnant during the course of the trial will be withdrawn and will be followed up until giving birth.

*Protocol violation*

Any participant found to have entered this study in violation of the protocol will be discontinued from the study at the discretion of the qualified investigator. This will include any participant found to have been inappropriately enrolled (did not meet eligibility criteria). Participant non-compliance includes failure to show up for study visits, failure to take the investigational product as directed, or refusal to undergo study visit procedures. Participants who are found to be taking prohibited medications or supplements without the knowledge of the qualified investigator will also be withdrawn. Any major protocol deviations (i.e. those that increase the risk to participants and/or compromise the integrity of the study or its results) will result in participant discontinuation.

*Participapnt Replacement*

For all early withdrawals, a participant leaving the study prematurely or in the event of participant removal will NOT be replaced by another. It is understood by all concerned that an excessive rate of withdrawals can render the study un-interpretable, thus unnecessary withdrawal of participants should be avoided.

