## 9 STUDY ASSESSMENTS

### 9.1 Screening (week -6 to -5; Visit 1) \*

\* At the discretion of the Qualified Investigator, any participants falling outside of the screening window (week -6 to -5) due to scheduling issues will be asked to repeat eligibility/screening procedures prior to randomization at baseline.

Participants will arrive at the clinic for screening assessments in a 12-hour or greater fasted state.

An informed consent form will be given to the potential volunteer. They will be required to read the information and will be given the opportunity to seek more information if needed, or the option of taking the consent form home to review prior to making their decision. If agreeable, the volunteer will sign the consent form and receive a duplicate of the signed copy. Once consent has been obtained, the screening visit will proceed. Each volunteer will be sequentially assigned a screening number to be entered in the screening and enrollment log.

Screening assessments include:

1. Review medical history, concomitant therapies, and daily exercise habits
2. Assess inclusion and exclusion criteria
3. Urine collection
  - a. Urine pregnancy test for female potential participants that are of child-bearing potential
  - b. Urinalysis (microscopy, chemical, urobilinogen/urine bilirubin)
4. Seated resting blood pressure, heart rate, respiratory rate, and temperature measurements
5. Weight, height (BMI calculation), waist circumference and hip circumference measurements
6. Body fat composition as determined by BIA
7. Collect fasted blood samples for analysis of CBC, Na, K, Cl, Fe, Mg, Ca, phosphate, HbA1c, fasting glucose, eGFR, creatinine, BUN, AST, ALT, GGT, ALP, TSH, total bilirubin, lipid profile, and fasting insulin
8. Dispense Three-Day Food Record (3DFR)
9. Dispense Daily Bowel Habits Diary
10. Dispense Exercise Diary
11. Dispense Subject Diary
12. Dispense stool collection kits

The next visit will be scheduled for potentially eligible participants for baseline (Week 0).

Reminders for participants prior to their next in-clinic visit:

1. Return to the clinic in a fasted state (12 hours or greater)
2. Abide by instructions for prescribed medications as per Section 7.3.1 and OTC medications, supplements, and food/drinks as per Section 7.3.2
3. Limit alcohol intake (<2 standard drinks per day or <10 per week)
4. Return stool collections
5. Complete and return Daily Bowel Habits Diary
6. Complete and return 3DFR Diary

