## 9.4 Baseline (Visit 2, Week 0)

Eligible participants (compliant with the exercise intervention and placebo consumption during the run-in period) will return to the clinic fasted for 12 hours with completed subject diaries, food records, daily bowel habit diaries, exercise diaries, and stool collections, for baseline assessments. Compliance calls will be made at fixed intervals (bi-weekly). Participants who have not provided a stool sample within 3 days of visit 2 and participants who have significant weight loss (> 0.7 kg/week) during the run-in period will be withdrawn from the study.

Baseline (Day 0) assessments include:

1. Review concomitant therapies and adverse events
2. Assess inclusion and exclusion criteria
3. Collect remaining placebo and calculate compliance
4. Physical examination
5. Collect and store stool samples
6. Collect and review Daily Bowel Habits Diary
7. Collect and review 3DFR
8. Collect and review Exercise Diary
9. Collect and review Subject Diary
10. Urine collection
  - a. Urine pregnancy test for female participants that are of child-bearing potential
  - b. Urinalysis (microscopy, chemical, urobilinogen/urine bilirubin)
11. Seated resting blood pressure, heart rate, respiratory rate, and temperature measurements
12. Weight (BMI calculation), waist and hip circumference measurements (waist/hip circumference ratio)

13. Randomization of eligible participants
14. Body fat composition as determined by BIA
15. DXA scan
16. Collect fasted blood samples for analysis of CBC, Na, K, Cl, Fe, Mg, Ca, phosphate, HbA1c, fasting glucose, eGFR, creatinine, BUN, AST, ALT, GGT, ALP, total bilirubin, lipid profile, and fasting insulin
17. Dispense investigational product and instruct participants on use
18. Dispense Daily Bowel Habits Diary
19. Dispense 3DFR
20. Dispense Exercise Diary
21. Dispense Subject Diary

The next visit will be scheduled for week 6.

Reminders for participants prior to their next in-clinic visit:

1. Return to the clinic in a fasted state (12 hours or greater)
2. Maintain exercise intervention (20 min aerobic exercise x 3 days/week)
3. Abide by instructions for prescribed medications as per Section 7.3.1 and OTC medications, supplements, and food/drinks as per Section 7.3.2
4. Limit alcohol intake (<2 standard drinks per day or <10 per week)
5. Complete and return Daily Bowel Habits Diary
6. Complete and return 3DFR Diary
7. Complete and return Exercise Diary
8. Complete and return Subject Diary
9. Return unused IP

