## **9.6 Visit 4 - End of Study (Week 12, 84 ± 3 days)**

Participants will return to the clinic fasted for 12 hours or greater with the unused product, in addition to completed subject diaries, food records, daily bowel habits diaries, exercise diaries, and stool collections, for assessments. Compliance calls will be made at fixed intervals.

Visit 4 assessments include:

1. Review concomitant therapies and adverse events
2. Return the unused investigational product in the original packaging and remnants; calculate compliance
3. Collect and store stool samples
4. Collect and review Subject Diary
5. Collect and review 3DFR
6. Collect and review Daily Bowel Habits Diary
7. Collect and review Exercise Diary
8. Urine collection
  - a. Urinalysis (microscopy, chemical, urobilinogen/urine bilirubin)
9. Seated resting blood pressure, heart rate, respiratory rate, and temperature measurements
10. Weight (BMI calculation), waist and hip circumference measurements (waist/hip circumference ratio)
11. Collect fasted blood samples for analysis of CBC, Na, K, Cl, Fe, Mg, Ca, phosphate, HbA1c, fasting glucose, eGFR, creatinine, BUN, AST, ALT, GGT, ALP, total bilirubin, lipid profile, and fasting insulin
12. DXA scan

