## **10.8 Dual-Energy X-Ray Absorptiometry (DXA) Scan**

The Dual-Energy X-Ray Absorptiometry Scan will be conducted at KGK clinic (London, ON) at visits 2 (week 0), and 4 (week 12) by trained technicians. Body tissue density will be measured by a form of X-ray radiation and converted into body fat and muscle mass percentage for assessment. Prior to the day of the DXA assessment, the coordinators will remind the participants to limit the amount of water and food consumption accordingly. A full body composition DXA scan will expose the participant to a total dose of <10uSV, depending on the size of the participant. This amount is less than a person is exposed to on an east to west coast flight within the USA and similar to the normal background radiation received over the course of a single day level (23, 24).

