### **10.13 Laboratory Analyses**

12 hours fasting blood samples will be drawn from the participants at screening (Visit 1), baseline visit (Visit 2), and at the End of Study visit (Visit 4) as indicated in the schedule of assessments in Section 1.3.

Protection of subject confidentiality will extend to all data generated from the assaying of these samples. These samples will be alphanumerically coded and the persons performing the analysis will not be aware of the subject's identity or the product they received.

**At screening (Visit 1),** 18 mL of 12 hour fasting whole blood will be collected in:

1. Two 4 mL EDTA vacutainer tubes for:
  - a. CBC analysis (One tube)
  - b. HbA1c analysis (one tube)
2. Two 5 mL SST vacutainer tubes to generate serum for:
  - a. Na, K, Cl, Fe, Ca, Mg, phosphate, fasting glucose, TSH, Lipid Panel, creatinine, eGFR, BUN, GGT, ALP, AST, ALT, and total bilirubin analysis (one tube)
  - b. Fasting Insulin (One tube)

Protocol 20BWHM:

A randomized, double-blind, placebo-controlled study to investigate the effects of a *Bifidobacterium breve* strain on fat loss in healthy adults

3. Urine will be collected for urine pregnancy test of women of childbearing potential and urinalysis

**At baseline (Visit 2),** 18 mL of 12 hours fasting blood will be collected in:

1. Two 4 mL EDTA vacutainer tubes for:
  - a. CBC analysis (one tube)
  - b. Hb1-Ac analysis (one tube)
2. Two 5 mL SST vacutainer tubes to generate serum for:
  - a. Na, K, Cl, Fe, Ca, Mg, phosphate, fasting glucose, Lipid Panel, creatinine, eGFR, BUN, GGT, ALP, AST, ALT, and total bilirubin analysis (one tube)
  - b. Fasting Insulin (One tube)
3. Urine will be collected for urine pregnancy test of women of childbearing potential and urinalysis.
4. Fecal Sample also will be collected for analysis

**At the end of the study (Visit 4),** 18 ml of 12 hours fasting blood will be collected in:

1. Two 4 mL EDTA vacutainer tubes for:
  - a. CBC analysis (one tube)
  - b. Hb1-Ac analysis (one tube)
2. Two 5 mL SST vacutainer tubes to generate serum for:
  - a. Na, K, Cl, Fe, Ca, Mg, phosphate, fasting glucose, Lipid Panel, creatinine, eGFR, BUN, GGT, ALP, AST, ALT, and total bilirubin analysis (one tube)
  - b. Fasting Insulin (One tube)
3. Urine will be collected for urinalysis
4. Fecal Sample also will be collected for analysis

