The total blood volume collection for the laboratory assessments listed above will be approximately 54 mL, over the period from screening to end of study. At any study visit, blood loss per volunteer is not expected to exceed 18 ml. Additional blood samples may be collected during the study in order to perform or repeat laboratory tests outlined in the Schedule of Assessments if needed.

Dynacare a central laboratory will be used in this study to measure blood parameters and urinalysis. Another lab will be used to process fecal samples.

Urine pregnancy test will be performed at the KGK Science clinic site.

Protocol 20BWHM:

A randomized, double-blind, placebo-controlled study to investigate the effects of a *Bifidobacterium breve* strain on fat loss in healthy adults

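### No urine pregnancy test is scheduled after Week 0, so at the Week-12 DXA the last scheduled test is 81–87 days old; a Visit 4 test before the scan would be a cheap precaution

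*Protocol*

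**What the plan says.** The rule on pregnancy is in Protocol 7.5, under removal by the qualified investigator: "Any female participant who becomes pregnant during the course of the trial will be withdrawn and will be followed up until giving birth". Section 11.1.2 adds that a birth defect in the child of a treated participant counts as a serious adverse event.

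Testing is described in three places, which agree:

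- **Schedule of Assessments (1.3).** The row "Urine pregnancy test" is marked at Visit 1 and Visit 2 (Week 0). It is blank at Visits 3 and 4.
- **Visit lists (9.1 to 9.6).** Screening has "Urine pregnancy test for female potential participants that are of child-bearing potential" and baseline has "Urine pregnancy test for female participants that are of child-bearing potential". Visit 3 lists no urine collection. At Visit 4 the only entry under urine collection is "a. Urinalysis (microscopy, chemical, urobilinogen/urine bilirubin".
- **Laboratory Analyses (10.13).** A pregnancy test is named at screening and baseline. For the end of study the entry is "3. Urine will be collected for urinalysis". The same section says "Urine pregnancy test will be performed at the KGK Science clinic site".

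Section 10.8 places the DXA scans "at visits 2 (week 0), and 4 (week 12) by trained technicians". The stated dose is below 10 µSv per scan, which the protocol likens to about a day of background radiation. Section 7.1 requires women of child-bearing potential to use approved contraception throughout, and 7.2 excludes women who are pregnant or planning pregnancy.

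**The concern.** The protocol places a duty on the site for any pregnancy that arises during the trial, and it can carry out that duty only once it knows of the pregnancy. At the first DXA visit a pregnancy test is on the list. At the second, after up to 12 weeks on product, it is not.

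Two things are at stake, both small. A woman with an unrecognised pregnancy could have an X-ray scan that would otherwise be held. Also, a pregnancy that began on product could come to light only after scheduled contact has ended, so that follow-up to birth starts late or is missed. This is a point about participant safety, not about the comparison of the two arms.

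**Working it through.** **1. Age of the last scheduled test at the second scan**

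Inputs: last scheduled test on Day 0 (9.4); Visit 4 window 84 ± 3 days (9.6).

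- Earliest: 84 − 3 = 81 days
- Latest: 84 + 3 = 87 days

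The documents do not state this figure, but it follows directly from the window.

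**2. Time from the scan to the last scheduled contact**

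Input: a telephone call at Week 14 (9.7), for which no window is given. Taking it as day 14 × 7 = 98:

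- 98 − 87 = 11 days
- 98 − 81 = 17 days

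The last scheduled contact is thus 11–17 days after the scan.

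**3. How a pregnancy could come to light after Day 0**

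| Route | Section | What it can reveal |
|---|---|---|
| Open question about problems, at each visit | 11.1.1 | A pregnancy the woman knows of or suspects |
| Bi-weekly calls on exercise, other therapies and product use | 9.3 | A volunteered report; possibly stopped hormonal contraception |
| Review of therapies and adverse events, Visits 3 and 4 | 9.5, 9.6 | The same |
| Daily diary | 17.2 | Free-text changes in health; item 7 asks only whether the menstrual cycle affected bowel movements |
| Week 14 call | 9.7 | A reported adverse event |

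None of these is a test. Most depend on the woman's own awareness. The therapy reviews are an indirect check and would not show whether barrier methods were being used.

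**4. Where an added test would act**

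| Added test | Age of last test at the Week-12 scan | Could shorten product exposure? |
|---|---|---|
| None (current plan) | 81–87 days | No |
| Visit 3 only (days 39–45) | 81 − 45 = 36 to 87 − 39 = 48 days | Yes, product is re-dispensed there |
| Visit 4, before the DXA | 0 days | No, dosing is complete |

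Visit 4 already has urine collection at item 8, listed ahead of the DXA at item 12, so a result can be available before the scan. Visit 3 would need a new urine sample.

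**5. Cost in data**

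One withheld scan is one Week-12 value out of 2 × 40 = 80 planned completers (12.1): 1/80 = 1.25%. The documents give neither the number of women of child-bearing potential nor a pregnancy rate, so no expected count is offered.

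**The case against.** The strongest reply is that the risk is already well controlled. Contraception is required for the whole study, hormonal methods must have been in use for at least three months, planned pregnancy is excluded, the dose is about one day of background radiation, and the product is a probiotic capsule. The investigator may order an unscheduled test at any time. The consent form and the site's DXA procedures were not available for this review, and a check before scanning may sit there. All of this stands, and it is why the point is minor.

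A reader might infer that the withdraw-and-follow rule in 7.5 cannot operate on a pregnancy not yet recognised. The documents do not support that. The rule covers any pregnancy that begins during the trial and sets no deadline for reporting, and the birth-defect criterion in 11.1.2 has no cut-off at Week 14. A pregnancy recognised later still falls under both. What is weaker is the chance that the site learns of it.

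A reader might also expect a Visit 4 test to protect against exposure to the product. It would not, because unused product is returned at that visit. Nor would it find every pregnancy, since a urine test can miss a very recent conception.

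Finally, a reader might see a fault in 7.5 because it asks for end-of-treatment evaluations at withdrawal and writes no DXA exception for pregnancy. Those evaluations are requested only where possible, so the investigator can already omit the scan.

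**Conclusion.** The gap in the schedule is real and is stated consistently in 1.3, in the visit lists and in 10.13, so it is not an artefact of one table. At the Week-12 DXA the last scheduled pregnancy test is 81–87 days old, and between Day 0 and that scan the site depends on self-report or indirect checks. Detection for the 7.5 rule is weakened, not disabled.

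The point is a minor safety precaution, worth considering because it costs so little. Few or no cases are to be expected, and no effect on the primary endpoint or on power is claimed. The conclusion rests on the schedule and the visit window alone. It is limited to scheduled tests in the protocol, and would lapse if the consent form or the site's DXA procedure already requires a test before the scan.

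**What to change.** Add a urine pregnancy test for women of child-bearing potential at Visit 4:

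- mark it at Visit 4 in the Schedule of Assessments (1.3);
- add it to item 8 of 9.6, to be read before the DXA;
- add it to the end-of-study list in 10.13, done on site with the urine already collected;
- state that if it is positive the DXA is omitted and follow-up to birth under 7.5 begins.

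The cost is one mark in the schedule, a line each in 9.6 and 10.13, and one test strip per woman of child-bearing potential. No new visit, sample, invasive procedure or staff is needed. The downside is that, rarely, a Week-12 DXA value will be missing by design and will fall under the missing-data rule in Protocol 12.3 and SAP section 7.

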#### *Compliance to exercise*

**Aerobic exercise** 20 minutes per day, 3 days a week

Weekly maximum score = 3 (compliant 3 days/week)

Compliance is calculated weekly by dividing the actual weekly score by the maximum weekly score multiplied by 100.

$$\frac{\text{actual score}}{3} \times 100\%$$

Participants found to have compliance of <80% will be counseled. Compliance of <70% will be considered as non-compliant and any participant demonstrating non-compliance for two consecutive weeks will be withdrawn from the study.

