### **11.2.2 Treatment and Follow-up of Laboratory Abnormalities**

In the event of participant-initiated withdrawal or clinically significant unexplained abnormal laboratory test values, the participant will be withdrawn from the treatment and will remain in the study and be required to attend all remaining study visits as part of a safety arm.

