### 12.2 Analysis Plan

The **Safety Population** will consist of all participants who received any amount of either product, and on whom any post-randomization safety information is available.

The **Intent-to-Treat (ITT) Population** consists of all participants who received either product and on whom any post-randomization efficacy information is available.

The **Per Protocol (PP) Population** consists of all participants who consumed at least 80% of treatment or placebo doses, do not have any major protocol violations and complete all study visits and procedures connected with measurement of the primary variable.

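### Withdrawal for deviations, prohibited products or exercise non-compliance also ends outcome collection, so ITT loses those participants' week-12 DXA on post-randomization grounds

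*Protocol*

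**What the plan says.** Protocol section 7.5 lists its rules as criteria for removal from the study. For undisclosed products: "Participants who are found to be taking prohibited medications or supplements without the knowledge of the qualified investigator will also be withdrawn". Major deviations that raise risk or "compromise the integrity of the study or its results) will result in participant discontinuation". Section 10.12 adds a rule for exercise compliance below 70%: "any participant demonstrating non-compliance for two consecutive weeks will be withdrawn from the study". Removed participants are not replaced.

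Section 7.5 also contains softer text. It opens with "Participant discontinuation should be considered at the discretion of the qualified investigator", and closes by asking that needless withdrawals be avoided because too many could leave the study impossible to interpret. It provides a partial safeguard: "If possible, the evaluations planned for the end of treatment will be carried out at the time when the participant is withdrawn from the study".

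Section 11.2.2 handles two other situations, participant-initiated withdrawal and unexplained clinically significant laboratory values. There the participant stops treatment but "will remain in the study and be required to attend all remaining study visits as part of a safety arm".

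On analysis, ITT (Protocol 12.2, SAP 3) keeps anyone who received product and has any efficacy data after randomization. PP requires at least 80% of doses and participants who "do not have any major protocol violations and complete all study visits" and procedures for the primary variable. Missing efficacy values are filled by LOCF or multiple imputation (Protocol 12.3, SAP 7). DXA is performed at weeks 0 and 12 only (Protocol 1.3 and 10.8).

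**The concern.** The purpose of ITT is to compare the arms as randomized, whatever participants did afterwards. The PP Population already deals with deviators by leaving them out, so nothing in the analysis requires that their outcomes go uncollected. Under sections 7.5 and 10.12, however, a participant who breaks the rules leaves the study, and no later visit exists at which the week-12 fat measurement could be taken.

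The triggers are events after randomization. Taking another weight-loss or probiotic product, or abandoning the exercise programme, may be related to how body weight is changing and possibly to the assigned arm. The missing values may therefore be informative. LOCF without an early scan records their fat change as zero. Multiple imputation fills the gap mainly from participants who complied. Either way, the primary ITT comparison leans on people who followed the protocol, and it does so for a reason that the trial itself creates.

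**Working it through.** **1. The plan's own figure.** Inputs from Protocol 12.1: 50 per arm, 20% attrition, SD 1.19 points and 1.24 kg, two-sided 5%, 80% power.
- Completers: 50 × (1 − 0.20) = 40 per arm.
- Two-sample t-test, 40 per arm: detectable differences 0.755 points and 0.787 kg, which round to the stated 0.76 and 0.79. Power at the stated values is 80.5% and 80.3%.

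The figure reproduces. It allows 10 losses per arm, not divided by reason.

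**2. Who keeps a week-12 DXA.**

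| Trigger | Place | Product stops | Remaining visits |
|---|---|---|---|
| Undisclosed prohibited product | 7.5 | yes (withdrawn) | none provided; scan at withdrawal where feasible |
| Major deviation | 7.5 | yes (discontinued) | same |
| Exercise below 70%, two weeks running | 10.12 | yes (withdrawn from study) | none provided; 7.5 scan at withdrawal where feasible |
| Participant-initiated withdrawal, unexplained laboratory values | 11.2.2 | yes | all, so Visit 4 with its DXA |
| Product compliance below 80% | 10.12 | no, counselled | all |

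The exercise trigger is easily met. The weekly score is out of 3, so one missed session gives 2/3 × 100 = 66.7%, which is below 70%. One missed session in each of two consecutive weeks is enough.

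**3. What LOCF does when there is no early scan.** The baseline DXA is carried forward, so change = 0. With mean changes mA and mP in those observed, and removed fractions fA and fP, the estimated difference is

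D = (1 − fA) × mA − (1 − fP) × mP.

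Equal removal f, with an observed difference of 0.76, gives D = (1 − f) × 0.76:
- f = 5%: 0.722
- f = 10%: 0.684
- f = 20%: 0.608

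Unequal removal, no true effect, same mean change m in both arms, fA = 20%, fP = 10%:
- m = −0.5: −0.40 − (−0.45) = 0.05
- m = −1.0: −0.80 − (−0.90) = 0.10

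These false differences are 0.05/0.76 = 7% and 0.10/0.76 = 13% of the planned detectable difference. They favour whichever arm loses fewer participants. All values of f and m are assumptions.

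**4. Would retention raise power?** Suppose 5 of the 10 planned losses per arm were scanned at week 12, giving 45 per arm, and that these 5 show a fraction k of the effect, with SD held at 1.19. The mean difference is (40 × 0.76 + 5 × k × 0.76)/45.

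| k | Difference | Power |
|---|---|---|
| 1 | 0.760 | 85.0% |
| 0.5 | 0.718 | 80.8% |
| 0 | 0.676 | 75.9% |

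Power exceeds the 80.5% at 40 per arm only if k is above about 0.47.

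**The case against.** Several stronger readings are tempting, and the documents do not support them.

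- A reader might infer that ITT turns into PP. It does not. ITT excludes nobody for deviations. A removed participant with any efficacy data after randomization stays in, with an early or imputed value. Participants below 80% of doses are only counselled, so they can reach week 12 and be in ITT but not in PP.
- A reader might infer that removed participants contribute only imputed values. Section 7.5 asks for the end-of-treatment evaluations at withdrawal where feasible, and these include DXA. But that scan is optional and is not a week-12 measurement.
- A reader might infer that every deviator must go. The discretion clause and the caution against needless withdrawal point the other way. The specific rules are nevertheless worded as mandatory, so the section conflicts with itself.
- A reader might infer that missed doses or visits lead to removal. Section 7.5 names them as non-compliance and attaches no consequence unless they are judged a major deviation. People who miss visits might not attend a week-12 scan under any wording.
- A reader might see section 11.2.2 as a direct contradiction. It covers different triggers and speaks of a safety arm, and different triggers may have different follow-up. What stands is that the protocol already accepts follow-up after product is stopped, and does not say why these cases differ.
- A reader might infer that the trial is underpowered. Section 12.1 gives one undivided 20% loss, which may already include these removals.

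**Conclusion.** The point holds in a limited form. As written, sections 7.5 and 10.12 end outcome collection for participants who deviate, take undisclosed prohibited products or fall short on exercise. Their week-12 primary outcome is then not observed. The ITT result depends on an optional earlier scan or on an imputation method that is still open, and the observed data shift toward compliant completers.

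The size cannot be fixed from the documents, because no removal rate is given. Under the illustrative assumptions above (no early scan, LOCF), equal removal of 10% to 20% dilutes 0.76 to between 0.684 and 0.608, and a 20% against 10% imbalance produces a false difference of 0.05 to 0.10 points. An early scan would change these figures, and so would multiple imputation.

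The case rests on bias from informative missingness. The sample size is not shown to be wrong, and retention improves power only if those retained keep about half or more of the effect.

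**What to change.** Reconcile Protocol sections 7.5 (including its own discretion clause and its caution about needless withdrawal), 10.12 and 11.2.2, so that each says whether stopping product also ends follow-up. The text should state that a protocol deviation, a prohibited product or exercise non-compliance is recorded and handled by exclusion from PP, and does not by itself end outcome collection.

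Ask such participants to attend the scheduled Visit 4 DXA if they still consent and the investigator sees no safety reason against it; pregnancy is one example of such a reason. State in SAP sections 3 and 7 that this value is analysed in ITT. Decisions on product and on clinical withdrawal stay with the investigator.

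The cost is a change of wording and a few more retained visits with a scan already in the schedule. The price in interpretation is that the ITT estimate will include some off-protocol exposure; PP remains the place where that exposure is excluded.
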